3.1 Background

In patients with insulin dependent diabetes mellitus, glycemic control is influenced by numerous factors such as insulin dosage, insulin absorption, timing, physiological/ lifestyle factors such as exercise, food intake, hormones and illness. These factors may contribute to significant variability in insulin requirements, which makes self-management of type 1 diabetes challenging.

Patients who are using continuous glucose monitoring (CGM), including sensor-augmented pump therapy, experience improvements in glycemic control. Advanced sensor-augmented insulin pumps are now being used in clinical practice including closed loop systems that automatically adjust the amount of insulin delivered to maintain glucose levels near the target value set by the user.¹

The MiniMed 780G system is a closed loop insulin system. In addition to automatically adjusting the amount of insulin delivered based on sensor glucose (SG) readings while operating in the SmartGuard feature, the MiniMed 780G insulin pump can also automatically deliver correction boluses when the system has been delivering at the maximum allowable basal rate and SG remains elevated. This pump is currently in commercial distribution in Canada, Australia, and the United States. Previous clinical investigations involved the 670G Version 4.0 pump (contains the 780G AHCL algorithm) used in combination with the Guardian Sensor (3) glucose sensor, Guardian Link 3 transmitter, Humalog and Novolog insulin. This investigation is intended to confirm safety and effectiveness of the 780G insulin pump used in combination with Fiasp insulin. Additional details for non-clinical/clinical testing are provided in the report of prior investigations/ Investigator's Brochure (IB).

3.2 Purpose

The purpose of this study is to evaluate the safety and effectiveness of the MiniMed 780G system in type 1 adult and pediatric subjects utilizing Fiasp (insulin aspart injection) in a home setting.

4. Objectives and Endpoints

4.1 Objectives

The objective of this study is to evaluate the safety and effectiveness of the MiniMed 780G system utilizing insulin Fiasp (insulin aspart injection) to support product and system labeling.

D00459338

Version E

4.2 Endpoints

Safety and effectiveness endpoints will be evaluated independently for ages 18-80 and ages 7-17.

4.2.1 Primary Safety Endpoint

- Age 18-80: The overall mean change in HbA1c from baseline to end of 3-month study period. The goal is to show non-inferiority with a margin of 0.4% comparing to a threshold of -0.5% in reducing HbA1c from baseline to end of 3-month study period.
- Age 7-17: The overall mean change in HbA1c from baseline to end of 3-month study period. The goal is to show non-inferiority with a margin of 0.4% comparing to a threshold of -0.38% in reducing HbA1c from baseline to end of 3-month study period.

4.2.2 **Primary Effectiveness Endpoint**

- Age 18-80: The mean % of time in range (TIR 70-180 mg/dL [3.9 -10.0 mmol/L]) will be estimated and compared to a threshold of 73.7% by a non-inferiority test with a margin of 7.5% and a significance level of 0.025 (one-sided).
- Age 7-17: The mean % of time in range (TIR 70-180 mg/dL [3.9 -10.0 mmol/L]) will be estimated and compared to a threshold of 65.3% by a non-inferiority test with a margin of 7.5% and a significance level of 0.025 (one-sided).

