8.3 Inclusion Criteria

- 1. Age 7 80 years at time of screening.
- 2. Has a clinical diagnosis of type 1 diabetes:
 - a. 14 80 years of age: A clinical diagnosis of type 1 diabetes for 2 years or more as determined via medical record or source documentation by an individual qualified to make a medical diagnosis.
 - b. 7 13 years of age: A clinical diagnosis of type 1 diabetes for 1 year or more as determined via medical record or source documentation by an individual qualified to make a medical diagnosis.

D00459338

- 3. Does not require a legally authorized representative to consent on their behalf due to mental or intellectual disability.
- 4. Subject or parent/caregiver is literate and able to read one of the languages offered in the pump.
- 5. Subject and/or legally authorized representative is willing to provide informed consent for participation.
- 6. Is willing to perform fingerstick blood glucose measurements as needed.
- 7. Is willing to wear the system continuously throughout the study.
- 8. Must have a minimum daily insulin requirement (Total Daily Dose) of greater than or equal to 8 units and maximum total daily dose of 250 units or less.
- 9. Has a Glycosylated hemoglobin (HbA1c) less than 10% (as processed by Central Lab) at time of screening visit.

Note: All HbA1c blood specimens will be sent to and tested by a National Glycohemoglobin Standardization Program (NGSP) certified Central Laboratory. HbA1c testing must follow NGSP standards.

- 10. Has thyroid-stimulating hormone (TSH) in the normal range OR if the TSH is out of normal reference range the Free T3 is below or within the lab's reference range and Free T4 is within the normal reference range.
- 11. Uses pump therapy for greater than 6 months prior to screening (with or without CGM experience)
- 12. Is willing to upload data from the study pump, must have Internet access, and a computer system, or compatible smartphone that meets the requirements for uploading the study pump.
- 13. Is willing to take one of the following insulins and can financially support the use of either of the 2 insulin preparations as required during the run-in period:
 - a. Humalog (insulin lispro injection)
 - b. NovoLog/NovoRapid (insulin aspart injection)
- 14. Is willing to take Fiasp insulin during the study period (supplied via Sponsor).

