14.5.1 Primary Safety Endpoint

Age 18-80:

 The overall mean change in HbA1c, Δµ_{780G}, from baseline to end of 3-month study period will be estimated and compared by a non-inferiority test to the threshold of -0.50% with a margin of 0.4%. A significance level of 0.025 (one-sided) will be used. Analysis will be performed on the ITT and PP populations.

The hypothesis of non-inferiority is mathematically expressed as:

H₀: $\Delta \mu_{780G} \ge -0.50\% + 0.4\%$ H_a: $\Delta \mu_{780G} < -0.50\% + 0.4\%$

Age 7-17:

• The overall mean change in HbA1c, $\Delta\mu_{780G}$, from baseline to end of 3-month study period will be estimated and compared by a non-inferiority test to the threshold of -0.38% with a margin of

CIP336 Clinical Investigation Plan Page 120 of 159 Medtronic D00459338 Version E Page 120 of 159 Medtronic

0.4%. A significance level of 0.025 (one-sided) will be used. Analysis will be performed on the ITT and PP populations.

The hypothesis of non-inferiority is mathematically expressed as:

 $H_0: \Delta \mu_{780G} ≥ -0.38\% + 0.4\%$

 $H_a: \Delta \mu_{780G} < -0.38\% + 0.4\%$

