7.5.2 Age 7-17

For the following endpoints from age 7-17, the procedure test hierarchically the ordered hypotheses in sequence at level $\alpha = 0.025$ until a first hypothesis is non-rejected.

Primary Safety Endpoint

 Age 7-17: The overall mean change in HbA1c from baseline to end of 3-month study period. The goal is to show non-inferiority with a margin of 0.4%⁴ comparing to a threshold of -0.38% in reducing HbA1c from baseline to end of 3-month study period.

Primary Effectiveness Endpoint

Age 7-17: The mean % of time in range (TIR 70-180 mg/dL [3.9 -10.0 mmol/L]) will be estimated and compared to a threshold of 65.3% by a non-inferiority test with a margin of 7.5%^{5,6} and a significance level of 0.025 (one-sided).

[figure not shown]
Secondary Effectiveness Endpoints

- Age 7-17: The mean % of time in hypoglycemia (< 54 mg/dL [3.0 mmol/L]) will be estimated and compared to a threshold of 0.71% by a non-inferiority test with a margin of 2%⁷ and a significance level of 0.025 (one-sided).
- Age 7-17: The mean % of time in range (TIR 70-180 mg/dL [3.9 -10.0 mmol/L]) will be estimated and compared to a threshold of 65.3% by a simple superiority test and a significance level of 0.025 (one-sided).

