7.9.1 Pass/Fail Criteria

- The goal of the study for each age cohort (age 18-80 and age 7-17) is to evaluate both primary safety and primary/secondary effective endpoints according to the predefined threshold per cohort. Once all effective endpoints are met, the claim of superiority will be made.
- The goal of study for each age cohort (age 18-80 and age 7-17) will be also considered met when the evaluation criteria of both primary safety and effective endpoints meets the predefined threshold per cohort. However, the claim of non-inferiority will not be made.

Justification for Exclusion of Particular Information from the testing of the Hypothesis: Not Applicable.

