7.9.2 Primary Safety Endpoint

Age 18-80:

[figure not shown]
The overall mean change in HbA1c, $\Delta\mu_{780G}$, from baseline to end of 3-month study period will be estimated and compared by a non-inferiority test to the threshold of -0.50% with a margin of 0.4%⁴. A significance level of 0.025 (one-sided) will be used. Analysis will be performed on the ITT and PP populations.

The hypothesis of non-inferiority is mathematically expressed as:

 H_0 : $\Delta \mu_{780G} \ge -0.50\% + 0.4\%$

 H_a : $\Delta \mu_{780G} < -0.50\% + 0.4\%$

17-JUN-2024 Revision 4.0 Page 19 of 25

The null hypothesis will be tested against the alternative hypothesis using one sample t test if normality assumption is met, Wilcoxon signed rank test if normality assumption is rejected. Non inferiority of MiniMed 780G system utilizing insulin Fiasp (insulin aspart injection) for age 18-80 will be concluded if null hypothesis is rejected.

Age 7-17:

The overall mean change in HbA1c, $\Delta \mu_{780G}$, from baseline to end of 3-month study period will be estimated and compared by a non-inferiority test to the threshold of -0.38% with a margin of 0.4%⁴. A significance level of 0.025 (one-sided) will be used. Analysis will be performed on the ITT and PP populations.

The hypothesis of non-inferiority is mathematically expressed as:

$$H_0$$
: $\Delta \mu_{780G} \ge -0.38\% + 0.4\%$

$$H_a$$
: $\Delta \mu_{780G} < -0.38\% + 0.4\%$

The null hypothesis will be tested against the alternative hypothesis using one sample t test if normality assumption is met, Wilcoxon signed rank test if normality assumption is rejected. Non inferiority of MiniMed 780G system utilizing insulin Fiasp (insulin aspart injection) for age 7-17 will be concluded if null hypothesis is rejected.

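### SAP 7.9.1 withholds the non-inferiority claim that SAP 7.9.2 and 7.9.3.1 say will be concluded when the primary tests pass, in both age cohorts

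*Protocol*

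**What the plan says.** Each cohort (18-80 and 7-17) has four tests in fixed order at one-sided 0.025 (SAP 7.5.1, 7.5.2): HbA1c non-inferiority, TIR non-inferiority, non-inferiority on time below 54 mg/dL, and TIR superiority. The first two are primary.

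The primary goal is stated as non-inferiority. Protocol 4.2.1 says for adults "The goal is to show non-inferiority with a margin of 0.4% comparing to a threshold of -0.5% in reducing HbA1c" and for ages 7-17 "The goal is to show non-inferiority with a margin of 0.4% comparing to a threshold of -0.38% in reducing HbA1c". Protocol 14.5.1 and SAP 7.5.2 and 7.9.2 repeat the pediatric figures.

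Four places say what follows from the results:

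- **SAP 7.9.2 (HbA1c)** ends each cohort's paragraph by stating that non-inferiority "for age 7-17 will be concluded if null hypothesis is rejected" (adult wording identical apart from the age range).
- **SAP 7.9.3.1 (TIR)** uses the same conclusion rule for both cohorts.
- **SAP 7.9.1, first bullet:** "Once all effective endpoints are met, the claim of superiority will be made".
- **SAP 7.9.1, second bullet:** the goal is also met when the primary safety and effectiveness endpoints meet their thresholds. It then adds: "However, the claim of non-inferiority will not be made".

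Protocol 14.5.2.1 bases success for each cohort on the two primary endpoints and attaches no restriction on what may be claimed.

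**The concern.** The second bullet of SAP 7.9.1 cannot be followed together with 7.9.2 and 7.9.3.1. A cohort that passes both primary tests has non-inferiority concluded twice, once per endpoint, and then has the claim withheld in the section that defines the study outcome. If it does not also pass every secondary effectiveness test, it earns no superiority claim either. It would be a success with nothing stated to conclude.

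The study's objective is to support labeling (Protocol 4.1), so the claim that follows from a pass should be settled before results are known. As the SAP stands, the choice between two contradictory sentences could be made afterwards.

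A smaller point concerns what a pediatric HbA1c pass means. The adult and pediatric goals share the same wording about reducing HbA1c, but the two bounds fall on opposite sides of zero.

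**Working it through.** **1. The passages applied to each outcome.** Within one cohort:

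| Result | Protocol 14.5.2.1 | SAP 7.9.2 / 7.9.3.1 | SAP 7.9.1 |
|---|---|---|---|
| A primary test fails | Not a success | Not concluded for that endpoint | Goal not met |
| Both primaries pass, time <54 mg/dL fails (TIR superiority not reached) | Success | Non-inferiority concluded | Goal met, non-inferiority claim withheld, no superiority claim |
| Both primaries and time <54 mg/dL pass, TIR superiority fails | Success | Non-inferiority concluded | Goal met, non-inferiority claim withheld, no superiority claim |
| All four pass | Success | Non-inferiority concluded | Superiority claimed; first bullet silent on non-inferiority |

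Rows two and three are the contradiction. Either secondary failure leads there, because the first bullet requires all effectiveness endpoints.

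**2. Bounds written in the hypotheses.**
- HbA1c, ages 7-17: -0.38 + 0.40 = **+0.02%**; margin/threshold = 0.40/0.38 = 105%.
- HbA1c, ages 18-80: -0.50 + 0.40 = -0.10%; margin/threshold = 0.40/0.50 = 80%.
- TIR: 65.3 - 7.5 = 57.8% (pediatric); 73.7 - 7.5 = 66.2% (adult).

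**3. Could rows two and three occur?** The TIR SD is not in the public text. Assume n = 100 and SD 8, 10 or 12 points, so SE = SD/10 = 0.8, 1.0 or 1.2.
- True TIR equal to the threshold: superiority fails with probability 1 - 0.025 = 97.5%, by construction. Non-inferiority is practically certain, since 7.5/1.2 = 6.25 standard errors even at the largest SD.
- True TIR 2 points above the threshold: noncentrality 2/SE = 2.5, 2.0 or 1.67. Non-inferiority passes and superiority fails in 30%, 49% or 62% of studies.

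These figures show only that the sentence would apply in plausible cases. They are not multiplied by the chance that HbA1c passes, and they leave out failure of the time <54 mg/dL test.

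**4. Pediatric HbA1c note.** By the one-sample t-test, a pass needs an observed mean below 0.02 - t(0.975, n-1) × SD/√n. With n = 100, t = 1.984 and assumed SDs (the SD is not public):

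| SD | Mean needed to pass | Mean needed to exclude zero | Pass probability if true change is 0 |
|---|---|---|---|
| 0.5 | -0.079 | -0.099 | 5.9% |
| 0.6 | -0.099 | -0.119 | 5.2% |
| 0.7 | -0.119 | -0.139 | 4.7% |
| 0.8 | -0.139 | -0.159 | 4.3% |

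In each row, observed means within a band 0.02 points wide pass with a two-sided 95% interval that includes zero.

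**The case against.** **It is probably a slip.** The bullet before it concerns superiority, and two SAP sections and the protocol all point the other way. A statistician running the analysis would likely read it as superiority, and no test, alpha level, order or pass/fail result would change. All of that stands, and it limits the size of the point. It does not remove it: the sentence is in the current SAP (Revision 4.0), in the section that defines the outcome, and nothing in the documents corrects it.

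**A claim may differ from a conclusion.** One could read 7.9.2 and 7.9.3.1 as statistical findings per endpoint and 7.9.1 as a rule on labeling claims. The documents draw no such distinction and do not say what would be claimed instead.

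**Stronger readings that the documents do not support:**
- *That pass/fail is undefined.* It is clear from Protocol 14.5.2.1, and 7.9.1 also counts the goal as met.
- *That the pediatric bound is an error and should move to zero.* It is written openly and consistently as a non-inferiority test on a safety endpoint, in subjects already treated ("Uses pump therapy for greater than 6 months prior to screening"), so a no-worsening bound is coherent. The 0.4% margin cites SAP reference 4. A bound of zero would replace it with an unsourced 0.38% for the sake of 0.02 points.
- *That the type I error is inflated.* A true change of zero lies inside the alternative hypothesis, so passing there is not a false rejection.
- *That pediatric HbA1c is nowhere compared with zero.* The public text skips sections (Protocol 4.2.3 to 4.2.5 and 14.5.2.2 to 14.5.4; SAP 7.9.4 to 7.9.7), so this absence cannot be established.

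**Conclusion.** The contradiction is real and covers both cohorts and both primary endpoints. SAP 7.9.1 withholds what 7.9.2 and 7.9.3.1 conclude, and it does not match Protocol 14.5.2.1. It takes effect when the primaries pass and either secondary effectiveness test does not. Its reach is the reported claim only. This rests on the wording alone and needs no assumed figure; the frequencies in step 3 depend on the assumed n, SD and true TIR. It should be corrected.

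The pediatric bound is an interpretive note, not a defect. A reader might infer from the goal's wording that a pass shows a fall in HbA1c. By itself it shows only that mean HbA1c did not rise by 0.02 points or more. The practical gap is small: at n = 100 and SD 0.5 to 0.8, a pass still needs an observed fall of about 0.08 to 0.14 points.

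**What to change.** In the second bullet of SAP 7.9.1, replace "However, the claim of non-inferiority will not be made" with:

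*In that case non-inferiority is concluded for the cohort (7.9.2, 7.9.3.1). The superiority claim is made only if the secondary effectiveness tests are also met in the order given in 7.5.*

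If the sponsor does mean to withhold the claim, 7.9.2 and 7.9.3.1 must change instead, and the SAP must say what a primary pass supports. Either way, settle it before the results are known.

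The cost of the replacement is one SAP sentence. It needs no new data or subjects and no change to any hypothesis, alpha level or test order. Protocol 14.5.2.1 already agrees with it.

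For the pediatric note, leave the hypothesis as it is. State in SAP 7.9.2 that a pass for ages 7-17 is not by itself evidence of a reduction, and report the two-sided 95% confidence interval for mean HbA1c change beside the test. SAP 7.2 already provides for such intervals where needed; this makes it definite here. It costs no power.

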4.2.3 Secondary Effectiveness Endpoint

- Age 18-80: The mean % of time in hypoglycemia (< 54 mg/dL [3.0 mmol/L]) will be estimated and compared to a threshold of 0.86% by a non-inferiority test with a margin of 2% and a significance level of 0.025 (one-sided).
- Age 18-80: The mean % of time in range (TIR 70-180 mg/dL [3.9 -10.0 mmol/L]) will be estimated and compared to a threshold of 73.7% by a simple superiority test and a significance level of 0.025 (one-sided).
- Age 7-17: The mean % of time in hypoglycemia (< 54 mg/dL [3.0 mmol/L]) will be estimated and compared to a threshold of 0.71% by a non-inferiority test with a margin of 2% and a significance level of 0.025 (one-sided).
- Age 7-17: The mean % of time in range (TIR 70-180 mg/dL [3.9 -10.0 mmol/L]) will be estimated and compared to a threshold of 65.3% by a simple superiority test and a significance level of 0.025 (one-sided).

4.2.5 Safety Data Summarized

Serious Adverse Events (SAE)

Serious Adverse Device Effects (SADE)

Unanticipated Adverse Device Effects

• Unanticipated Serious Adverse Device Effect Incidence of Severe Hypoglycemia

Incidence of Severe Hyperglycemia

Incidence of DKA

CIP336 Clinical Investigation Plan Medtronic D00459338 Version E Page 33 of 159

4.2.6 **Device Deficiencies**

Descriptive summary will be used to characterize DDs:

• All reports of device issues.

5. Study Design

This global study is a multi-center, single arm study in insulin-requiring adult and pediatric subjects with type 1 diabetes on the MiniMed 780G system using Fiasp insulin as well as Medtronic Extended infusion set and reservoir. The run-in period and study period will be approximately 120 days long.

The period from Visit 1 (consent and screening) through Visit 6 should be completed in 30 days.

Companions:

Subjects will be required to have a companion who resides (or will live) in the same building (or home) during the study at night, and also to be physically present in the same building, home or location (if not at home) during the exercise and meal challenges. A companion should be present during meal challenges and for 4 hours following the start of the meal. Companions should be able to check SMBG, give glucose and/or administer glucagon.

Run-in Period (Visits 2-6):

The run-in period begins at Visit 2 and ends once Visit 7 occurs.

The intent of the run-in period will be to allow subjects to become familiar with new study devices while using their own insulin, either Humalog[™] (insulin lispro injection) or NovoLog[®]/NovoRapid[®] (insulin aspart solution for injection). During the run-in period, study subjects with prior Automated Insulin

D00459338 Version E Page 34 of 159		Medtronic
------------------------------------	--	-----------

Delivery (AID) control algorithm experience will be using the study pump with the SmartGuard feature activated (Auto Correction must remain OFF). and Medtronic Extended infusion set and reservoir. Subjects who do not have prior AID algorithm experience will use the system in Manual Mode. Before and during run-in period meal challenges, SmartGuard must be turned OFF, as noted in Meal Challenge instructional materials.

Note for subjects who have prior experience with the Auto Mode feature in Medtronic pumps (670G/770G): The term "Auto Mode" has been replaced by the term "SmartGuard" in the 780G pump.

During the run-in period, a 120 mg/dL (6.7 mmol/L) Auto Basal target should be set. It is recommended that Active Insulin Time is set to 4 hours.

Note: The Auto Basal target setting and Active Insulin Time should be set as recommended above, unless there is a documented safety reason that would not permit these settings to be used.

All subjects and their parents/caregivers as well as companions will be trained on diabetes management principles, such as the treatment of hyperglycemia and hypoglycemia. In addition, there will be training regarding the need to have access to and how to use glucose and glucagon in case of hypoglycemia.

Parents/caregivers and companions will be instructed that they should be with the subject in the same residence or building overnight.

If the MiniMed Clinical app/MiniMed Mobile app and the CareLink Clinical app are being used, parents/caregivers will be instructed that subjects should be connected to CareLink via the appropriate Smartphone app for data uploading and push notifications for low or high blood sugar when they are apart, e.g., at school, other activities. Instructions on the appropriate operation of the apps will be provided.

For study purposes, subjects, companions, and parents/caregivers will be trained and/or instructed to perform self-monitoring of blood glucose (SMBG) if subjects are experiencing a severe hypoglycemic event, severe hyperglycemic event or diabetic ketoacidosis (DKA). Subjects and their parents/caregivers as well as companions will also be instructed to check blood ketones using a ketone meter if the Accu-Chek Guide Link study meter reading is greater than 300 mg/dL (16.7 mmol/L).

As a precaution, subjects and their parents/caregivers will be told that they should keep their own insulin pump supplies in a safe place and to have back up supplies on hand (such as insulin and syringe, or insulin pen) in the event they are asked to revert back to their own therapy during the study or experience study pump issues (i.e., infusion set occlusion with high glucose).

Subjects and their parents/caregivers will be instructed to insert sensors only in the locations that are specified in the User Guide materials. Reminders will be given to subjects at each office visit. Information about sensor insertions will be collected on an electronic case report form (eCRF) in the study database, i.e., insertion location.

D00459338

Version E

Subjects and their parents/caregivers will be trained on all parts of the device system. This training may include access to and use of digital online learning content. A training checklist for both subjects and parents/caregivers will be implemented and completed.

The completion of emergency response training, including the use of a ketone meter, will be documented for companions. Companions may be trained in person or remotely.

After completion of training on the study devices, subjects and their parents/caregivers may attend additional visits in the days immediately following the start of system use, as needed. They may also take advantage of having access to the digital learning content.

Study Period (Visits 7-15):

All subjects will use Fiasp for the remainder of the study and will continue using the study pump, with SmartGuard feature enabled (including Auto Correction), infusion set and reservoir for approximately 90 days during the study period.

Subjects should use the system with the SmartGuard feature turned on at all times with Fiasp. When prompted by the pump, subjects should take appropriate measures and follow directions on the pump to remain in or return to the SmartGuard feature. During times when subjects are not able to use the SmartGuard feature, they should use the system in Manual Mode (e.g., Suspend before low and Suspend on low).

During the first 3 weeks (between Visits 7 and 11) of the study period, a 120 mg/dL (6.7 mmol/L) Auto Basal target should be set. It is recommended that Active Insulin Time is initially set to 4 hours and then titrated towards 2-3 hours or at the investigator's discretion.

During the next 3 weeks (between Visits 11 and 13) of the study period, the Auto Basal target setting should be set to 100 mg/dL (5.5 mmol/L). Active Insulin Time is recommended to be set to 2-3 hours or at investigator's discretion.

During the remaining weeks of the study (any time after Visit 13) of the study period, the Auto Basal target as well as Active Insulin Time should be set to what is best for the individual subject, at investigator's discretion.

Note: The Auto Basal target setting and Active Insulin Time should be set as recommended above, unless there is a documented safety reason that would not permit these settings to be used.

After completion of training on the SmartGuard function, subjects and their parents/caregivers may attend additional visits in the days immediately following the start of SmartGuard use, as needed. They may also take advantage of having access to the digital learning content.
Version E Page 36 of 159

Staged Enrollment:

D00459338

The enrollment of subjects 7-17 years of age will not move forward until 10 subjects 18 years or older have completed 30 days of the study period and the Data Monitoring Committee (DMC) has determined that it is safe for 7-17 year olds to be enrolled into the study.

SMBG recommendations for 780G system:

With the 780G system and the Guardian 4 CGM, calibration is not required. However, a calibration is optional and will occur any time a blood glucose (BG) is entered. Occasionally, subjects may receive a notification if the pump needs a BG to enter or stay in the SmartGuard feature. Subjects will be instructed to perform SMBG if their symptoms do not match the sensor glucose (SG) value (i.e., they develop symptoms of hypoglycemia or hyperglycemia, but the SG value does not correlate with their symptoms).

Meal and Exercise Challenges:

All subjects will be asked to participate in meal and exercise challenges during the run-in and study period.

- All challenges are at least 4 hours in duration, beginning from the time when the challenge meals or exercise are started.
- There should not be more than one meal challenge on a single day.
- Meal and exercise challenges should not be scheduled on the same day during the specified time periods.

For example: A study period regular sized or large sized meal challenge should not take place on the same day as an exercise challenge.

Subjects will be asked to check BG at the start of the meal/exercise, as well as 2 hours and 4 hours after the start of the meal/exercise and provide correction insulin as necessary.

Throughout the study, it is important for subjects to avoid additional meal/snack or exercise up to four hours after the start of the challenge. If additional meal/snack or exercise is needed within 4 hours after the start of the challenge, the subject will acknowledge that food intake or exercise occurred. Content and timing of the meal and exercise, along with BG values, will be recorded on a log provided by the study team.

Meal challenges for all subjects (Run-in and Study period):

The following meal challenges are required during the run-in and study periods:

- Two meal challenges during the run-in period with subjects using the system in Manual Mode between Visits 5 and 7
 - o Regular sized meal with missed meal bolus at lunch

D00459338

Version E

- Large sized meal at breakfast, lunch or dinner
- Two meal challenges during the study period with subjects using the system in SmartGuard, Auto Basal target set at 120 mg/dL (6.7 mmol/L) between Visits 9 and 11 of study period
 - o Regular sized meal with missed meal bolus at lunch
 - Large sized meal at breakfast, lunch or dinner
- Two meal challenges during the study period with subjects using the system in SmartGuard, Auto Basal target set at 100 mg/dL (5.5 mmol/L) between Visits 12 and 13 of study period
 - Regular sized meal with missed meal bolus at lunch
 - Large sized meal at breakfast, lunch or dinner
- One meal challenge during the study period with subjects using the system in SmartGuard, Auto Basal target set at currently set Auto Basal target at any time after Visit 13 of study period
 - Large sized meal at breakfast, lunch or dinner

Meal challenges should only start if the following conditions are met:

- SMBG at start of meal is < 200 mg/dL (11.1 mmol/L)
- Sensor glucose is available.

Timing	Settings/Conditions	Meal Size	Meal Type	Notes
Run-in Period between visits 5 and 7	Manual Mode only Missed meal bolus	Regular sized meal	Lunch	Meal content, meal size and time of meal consumption should be established so that regular sized meal challenges during the study period can be matched
Run-in Period between visits 5 and 7	Manual Mode only	Large sized meal	Breakfast Lunch or Dinner	Meal content, meal size and time of meal consumption should be established so that large sized meal challenges during the study period can be matched
Study Period, between Visits 9 and 11	SmartGuard (120 mg/dL [6.7 mmol/L] setpoint) Missed Meal bolus	Regular sized meal	Lunch	Meal content, meal size and time of meal consumption should match regular meal taken during run-in and the regular meal taken at the 100 mg/dL (5.5 mmol/L) setpoint
Study Period, between Visits 9	SmartGuard (120 mg/dL [6.7 mmol/L] setpoint)	Large sized meal	Breakfast, Lunch or Dinner	Meal content, meal size and time of meal consumption should match meal at Setpoint

D00459338		Version E		Page 38 of 159
and 11				of 100 mg/dL (5.5 mmol/L) and run-in period meal
Study Period, between Visits 12 and 13	SmartGuard (100 mg/dL [5.5 mmol/L] setpoint) Missed meal bolus	Regular sized meal	Lunch	Meal content, meal size and time of meal consumption should match regular meal taken during run-in and the regular meal taken at the 120 mg/dL (6.7 mmol/L).
Study Period, between Visits 12 and 13	SmartGuard (100 mg/dL [5.5 mmol/L] setpoint)	Large sized meal	Breakfast Lunch or Dinner	Meal content, meal size and time of meal consumption should match meal at Setpoint of 120 mg/dL (6.7 mmol/L) and run-in period large sized meal
Study Period Any time after Visit 13	SmartGuard (with current Auto Basal target setpoint)	Large sized meal	Breakfast Lunch or Dinner	Meal content, meal size and time of meal consumption should match large meal at Setpoint of 120 mg/dL (6.7 mmol/L)/100 mg/dL (5.5 mmol/L) and run-in period large sized meals

Regular Sized Meal Challenge with Missed Meal Bolus:

Between Visits 5 and 7 for the run-in period, while subjects are in Manual Mode with CGM, they will be asked to consume a meal without administration of a Meal Bolus at lunch. The size of the meal should be equivalent to what subjects would normally eat at this mealtime.

During the study period, once at each Auto Basal setpoint (i.e. 120 mg/dL[6.7 mmol/L] and 100 mg/dL[5.5 mmol/L]), subjects will be asked to consume the same regular sized lunch meal that they had during the run-in period. For example, if the regular sized meal was consumed without an insulin bolus for the meal at 12 pm during the run-in period, that same regular sized meal should be consumed at approximately the same time of day at each setpoint during the study period.

Large sized Meal Challenges:

On large sized meal challenge days, subjects will be instructed to eat at least 1 meal with at least 50% higher caloric intake including 50% more carbohydrates and 50% higher in fat. It is recommended that subjects eat food at restaurants or consume prepared meals. The FoodPrint[™] phone app (as well as questions that will be asked by the investigational center staff during visits following meal challenges) will be used to collect information about type of food, name of restaurant (if applicable), subject confirmation that the meal eaten was different from any meal eaten within the last month and subject confirmation

Medtronic Business Restricted

Medtronic

CIP336 Clinical Investigation Plan			
D00459338	Version E	Page 39 of 159	Medtronic

that meal size was at least 50% more than when subjects usually consume in terms of calories, carbohydrates and fat. The timing of the meal challenges will be at the investigator's discretion. The subject's parent/caregiver should be physically present in the same building, home or location (if not at home) during the meal challenge (and for 4 hours following the start of the meal), must be able to check SMBG (in case it is needed), and give glucose/administer glucagon as needed.

Exercise Challenge for all subjects (Study Period only):

The following exercise challenges are required during the study period:

- 2 exercise challenges at setpoint of 120 mg/dL (6.7 mmol/L, between Visits 9 and 11 of the study period)
- 2 exercise challenges at setpoint of 100 mg/dL (5.5 mmol/L, between Visits 12 and 13 of the study period)
- 1 exercise challenge at currently set Auto Basal target, at any time after Visit 13 of the study period

Conditions at start of the exercise challenges:

- SG should be present at the start of each exercise challenge
- The investigator or his/her staff will determine the minimum BG for each subject at the start of each exercise challenge. It will be noted on the subject's exercise log.

Timing	Settings/Conditions	Exercise duration	Notes
Study Period, between Visits 9 and 11	SmartGuard (120 mg/dL [6.7 mmol/L] setpoint)	Min 30 minutes, up to 1.5 hours	Challenge must take place on days without meal challenge
Study Period, between Visits 9 and 11	SmartGuard (120 mg/dL [6.7 mmol/L] setpoint)	Min 30 minutes, up to 1.5 hours	Challenge must take place on days without meal challenge
Study Period, between Visits 12 and 13	SmartGuard (100 mg/dL [5.5 mmol/L] setpoint)	Min 30 minutes, up to 1.5 hours	Challenge must take place on days without meal challenge

CIP336 Clinical Investigation Plan				
D00459338		Version E	Page 40 of 159	Me
Study Period, between Visits 12 and 13	SmartGuard (100 mg/dL [5.5 mmol/L] setpoint)	Min 30 minutes, up to 1.5 hours	Challenge must take place on days without meal challenge	
Study Period Any time after Visit 13	SmartGuard (with current Auto Basal target setpoint)	Min 30 minutes, up to 1.5 hours	Challenge must take place on days without meal challenge	

edtronic

Exercise Challenges Details:

To fulfill the exercise challenge requirement, subjects will be asked to engage in 0.5 up to 1.5 hours of physical exercise. During this time, subjects should use either the Auto Basal setpoint target of 100 mg/dL (5.5 mmol/L) or 120 mg/dL (6.7 mmol/L) (depending on what is required at that time of the study period) unless a subject prefers to use the 150 mg/dL (8.3 mmol/L) target before, during and immediately after the exercise challenges. The FoodPrint[™] phone app (as well as questions that will be asked by the investigational center staff during visits following exercise challenges) will be used to collect information about exercise type, date, time (start and finish of exercise), duration and name of the parents/caregivers/ companion present. The timing of the exercise challenges to indicate where the exercise took place. Subjects may also use a Smartphone app to document their exercise. The subject's parents/caregivers/companion must be physically present in the same building, home or location (if not at home) during the exercise challenge, must be able to check SMBG (in case it is needed) and give glucose/administer glucagon as needed. Examples of types of exercise include, but are not limited to:

- Running
- Cycling
- Swimming
- Hiking
- Walking
- Games (e.g. Wii interactive video games)
- Indoor/outdoor playground (Pediatric subjects)
- Yoga/stretching
- Any sport activity that involves ongoing physical movement (e.g., tennis, golf, basketball, volleyball, soccer)
- Dancing

CIP336 Clinical Investigation Plan				
D0045933	38	Version E	Page 41 of 159	Medtronic
•	Zumba			
•	Aerobics			
•	Spinning			

